5. TREATMENT PLAN

Figure 1. Treatment Schema

This is a phase IB/II study that will investigate the combination of Ibrutinib with GA101 – Obinutuzumab in previously untreated CLL subjects \geq 65 years of age or subjects < 65 years that either refuse to be treated with chemotherapy or that are not candidates for treatment with chemotherapy agents.

Treatment will be given up to 6 cycles, each cycle will have duration of 28 days (Figure 1 - Appendix 2).

Ibrutinib will be given at 420 mg po daily during the complete study period (6 cycles) and will continue during the following 3 years until unacceptable toxicity

Ibrutinib + GA101 – Obinutuzumab. University of California, San Diego

or CLL progression in those subjects who respond to treatment. The first dose will be delivered in the clinic on Day 1, one to three hours before the GA101 – Obinutuzumab infusion, after which the subsequent dosing will be on an outpatient basis.

GA101- Obinutuzumab will be given at 1,000 mg / dose. The first dose given on cycle 1 will be split in 2 doses - Day 1 dose of 100mg and Day 2 dose of 900 mg. Subsequent doses of GA101 - Obinutuzumab (1,000 mg) will be administered on Cycle 1 - Days 8, 15; and on Day 1 of Cycles 2-6 (study days 29, 57, 85, 113, 141).

This research study protocol allows the subject to receive up to 8 infusions of GA101- Obinutuzumab. Even if the treatment is shown to be of benefit, additional infusions of GA101- Obinutuzumab beyond that allowed in the protocol cannot be given to the subject while they are participating in this study.

6. STUDY MEDICATIONS

6.1 IBRUTINIB

6.1.1 Formulation

Ibrutinib will be supplied as hard gelatin 140-mg capsules for oral (PO) administration. **Pharmacyclics** will provide Ibrutinib during the complete study period (6 cycles) and after cycle 6, during the following 3 years.

6.1.2 Dosage and Administration

Ibrutinib 420 mg (3 x 140-mg capsules) is administered orally once daily with 8 ounces (approximately 240 mL) of water. The capsules should be swallowed intact and subjects should not attempt to open capsules or dissolve them in water. Each dose of Ibrutinib should be taken approximately at the same time each day. The use of CYP3A4/5 inhibitors/inducers, CYP2D6 inhibitors, and grapefruit and Seville oranges (due to CYP3A4/5 inhibition) should be avoided for the duration of the study (appendix 5).

If a dose is missed, it can be taken up to 6 hours after the scheduled time with a return to the normal schedule the following day. If the dose is more than 6 hours late, the dose should not be taken and the subjects should take the next dose at the scheduled time the next day. Missed doses should be recorded by the subjects in the drug diary.

The first dose will be delivered in the clinic on Day 1, one to three hours before the GA101 – Obinutuzumab infusion, after which subsequent dosing is typically on an outpatient basis. Ibrutinib will be dispensed to subjects in bottles at each visit. Unused Ibrutinib dispensed during previous visits must be returned to the site and drug

Ibrutinib + GA101 – Obinutuzumab. University of California, San Diego

accountability records updated at each visit. Returned capsules must not be redispensed to anyone.

After cycle 6, Ibrutinib will be administrated during the following 3 years until unacceptable toxicity or CLL progression and will be dispensed in bottles every 3 or 6 months at each follow-up visit.

6.2 GA101 - OBINUTUZUMAB

6.2.1 Formulation

GA101 - Obinutuzumab is provided as a single-use vial. Each vial contains a sterile liquid formulation in a 50-mL pharmaceutical-grade glass vial containing a nominal dose of 1,000 mg of GA101 - Obinutuzumab (G3 material). The formulated drug product consists of 25 mg/mL drug substance formulated in histidine/histidine-HCl, trehalose, and poloxamer 188. The vial contains 41 mL (with 2.5% overfill).

GA101 – Obinutuzumab will be requested to be covered by the insurance as a Standard of Care treatment for previously untreated subjects.

6.2.2 Storage

The recommended storage conditions for the GA101-Obinutuzumab drug product are between 2°C and 8°C, protected from light. Chemical and physical in-use stability for GA101-Obinutuzumab dilutions in 0.9% sodium chloride (NaCl) at concentrations of 0.2 – 20 mg/mL have been demonstrated for 24 hours at 2°C – 8°C and an additional 24 hours at ambient temperature and ambient room lighting. The prepared diluted product should generally be used immediately. If not used immediately, in-use storage times and conditions prior to use are the responsibility of the user and would normally not be longer than 24 hours at 2°C – 8°C unless reconstitution/dilution has taken place in controlled and validated aseptic conditions. GA101 - Obinutuzumab should not be frozen or shaken. Mix gently. All transfer procedures require strict adherence to aseptic techniques. Do not use an additional in line filter because of potential adsorption.

6.2.3 Preparation

Split dosing: Splitting the first dose of GA101-Obinutuzumab in Cycle 1 is mandatory. The first dose (1,000 mg) must be administered over Days 1 and 2 (100 mg on Day 1 and 900 mg on Day 2).

GA101 - Obinutuzumab drug product intended for IV infusion is prepared by dilution of the drug product into an infusion bag containing 0.9% NaCl.

Ibrutinib + GA101 - Obinutuzumab. University of California, San Diego

One vial may be used to prepare both the 100-mg dose (equals 4 mL) and 900-mg dose (equals 36 mL) following the directions below. If both bags are prepared at the same time, the reconstitution/dilution has to take place in a controlled and validated aseptic conditions. Subsequently store the 900-mg bag for a maximum of 24 hours at $2^{\circ}\text{C} - 8^{\circ}\text{C}$ and administer the next day.

To prepare a 100-mg dose: The final drug concentration of a 100-mg dose should be in the range of 0.4 mg/mL to 4.0 mg/mL. Using a 250-mL infusion bag containing 0.9% NaCl withdraw 4 mL of GA101-Obinutuzumab from a single glass vial and inject it into the infusion bag (discard any unused portion of GA101-Obinutuzumab left in the vial unless reconstitution/dilution has taken place in controlled and validated aseptic conditions). Gently invert the infusion bag to mix the solution. Do not shake.

To prepare a 900-mg dose: The final drug concentration of a 900-mg dose should be in the range of 0.4 mg/mL to 4.0 mg/mL. Using a 250-mL infusion bag containing 0.9% NaCl withdraw 36 mL of GA101-Obinutuzumab from a single glass vial and inject it into the infusion bag (discard any unused portion of GA101-Obinutuzumab left in the vial unless reconstitution/dilution has taken place in controlled and validated aseptic conditions). Gently invert the infusion bag to mix the solution. Do not shake.

To prepare a 1,000-mg dose: The final drug concentration of a 1,000-mg dose should be 4 mg/mL. Using a 250-mL infusion bag containing 0.9% NaCl withdraw 40 mL of GA101-Obinutuzumab from a single glass vial and inject it into the infusion bag (discard any unused portion of GA101-Obinutuzumab left in the vial). Gently invert the infusion bag to mix the solution. Do not shake.

Administration sets with polyvinyl chloride, polyurethane, or polyethylene as product contact surface and IV bags with polyolefin, polypropylene, polyvinyl chloride, or polyethylene as product contact surface are compatible and may be used. Use of a port or peripherally inserted central catheter line is acceptable.

Do not use GA101 - Obinutuzumab beyond the expiration date stamped on the carton.

6.2.4 Dosage and Administration

GA101 - Obinutuzumab administered by IV infusion for up to 6 cycles (28-day cycles):

- On Cycle 1, Day 1, 100 mg GA101-Obinutuzumab will be administered
- On Cycle 1, Day 2, 900 mg of GA101-Obinutuzumab will be administered

Ibrutinib + GA101 - Obinutuzumab. University of California, San Diego

- On Cycle 1, Days 8 and 15, 1,000 mg of GA101-Obinutuzumab will be administered.
- On Cycles 2 6, Day 1, 1,000 mg of GA101-Obinutuzumab will be administered (See Table 1).

GA101 - Obinutuzumab $\underline{\text{must}}$ be administered in a clinical setting (inpatient or outpatient). Full emergency resuscitation facilities should be immediately available, and Subjects should be under close supervision by the investigator at all times. GA101-Obinutuzumab should be given as a slow IV infusion through a dedicated line. IV infusion pumps (such as Braun Infusomat Space) should be used to control the infusion rate of GA101-Obinutuzumab. Do not administer as an IV push or bolus. After the end of the infusions, the IV line should remain in place for 1 hour \pm 30 minutes from the end of infusion; if no AEs occur after 1 hour \pm 30 minutes, the IV line may be removed.

6.2.5 Premedication Requirements

Infusion-Related Reactions

Since some subjects may develop hypersensitivity or other IRRs to GA101 - Obinutuzumab, pre-medication is recommended to reduce the risk of infusion reactions as outlined below (Figure 2):

[figure not shown]
- Cycle 1, Days 1 and 2, all subjects require pre-medication with:
 - IV glucocorticoid: dexamethasone (20 mg) or methylprednisolone (80 mg) administered at least one hour prior to GA101-Obinutuzumab infusion.
 Hydrocortisone should not be used as it has not been effective in reducing rates of IRR.
 - An oral acetaminophen (975 mg) and an antihistamine such as diphenhydramine (50 mg) administered at least 30 minutes before starting each GA101-Obinutuzumab infusion.
- Cycle 1, Days 8 and 15 and Cycles 2-6, Day 1:
 - All subjects require pre-medication with oral acetaminophen (975 mg) administered at least 30 minutes before starting each GA101-Obinutuzumab infusion.
 - Subjects who experience an IRR (Grade 1 or more) with the previous infusion will require pre-medication with an antihistamine such as diphenhydramine (50 mg) administered at least 30 minutes before starting each subsequent GA101-Obinutuzumab infusion.
 - Subjects who experience a Grade 3 IRR with the previous infusion or who have lymphocyte counts of ≥ 25 × 10⁹/L prior to the next treatment will require pre medication with IV glucocorticoid: dexamethasone (20 mg) or methylprednisolone (80 mg) administered at least one hour prior to GA101-Ibrutinib + GA101 Obinutuzumab. University of California, San Diego

Obinutuzumab infusion. Hydrocortisone should not be used as it has not been effective in reducing rates of IRR.

Hypotension may be expected to occur during GA101-Obinutuzumab infusions. Withholding of antihypertensive treatments should be considered for 12 hours prior to and throughout each GA101-Obinutuzumab infusion and for the first hour after administration. Subjects at acute risk of hypertensive crisis should be evaluated for the benefits and risks of withholding their hypertensive medication.

For TLS prophylaxis, see Section 6.2.12

Figure 2. Recommended Premedication to Reduce Infusion-related Reactions.

- ^a Hydrocortisone is not recommended, as it has not been effective in reducing rates of infusion reactions.
- ^b Glucocorticoid administration to be completed at least 1 hour prior to GA101 Obinutuzumab infusion.
- ^c Acetaminophen and antihistamine at least 30 minutes prior to GA101 Obinutuzumab infusion.

6.2.6 Split Dosing

On Cycle 1, Day 1, 100 mg GA101-Obinutuzumab will be administered. On Cycle 1, Day 2, 900 mg of GA101-Obinutuzumab will be administered. On Cycle 1, Ibrutinib + GA101 – Obinutuzumab. University of California, San Diego

Days 8 and 15, and Day 1 of Cycles 2-6, 1,000 mg of GA101-Obinutuzumab will be administered (see Table 1).

Table 1 GA101 - Obinutuzumab Dosing Schedule

Cycle and Day of Administration		Dose of Obinutuzumab	Rate of Infusion (in the Absence of Infusion Reactions/ Hypersensitivity during Previous Infusions)	
	Day 1 100 m		Administer at 25 mg/hour over 4 hours. Do not increase the infusion rate.	
Cycle 1	Day 2	900 mg	Administer at 50 mg/hour. The rate of the infusion can be escalated in increments of 50 mg/hour every 30 minutes to a maximum rate of 400 mg/hour.	
,	Day 8	1,000 mg		
	Day 15	1,000 mg	Infusions can be started at a rate of 100 mg/hour and increased by 100 mg/hour	
Cycles 2–6	Day 1	1,000 mg	increments every 30 minutes to a maximum 400 mg/hour.	

If a subject experience any grade infusion reaction during infusion, adjust the infusion as outlined below:

- Grade 4 (life threatening): Stop infusion and discontinue therapy.
- Grade 3 (severe): Temporarily interrupt infusion and treat symptoms. Upon resolution of symptoms, restart infusion at no more than half the previous rate (the rate being used at the time that the infusion reaction occurred) and, if subject does not experience any infusion reaction symptoms, infusion rate escalation may resume at the increments and intervals as appropriate for the treatment dose.
- Grade 1 2 (mild to moderate): Reduce infusion rate and treat symptoms. Upon resolution of symptoms, continue infusion and, if subject does not experience any

Ibrutinib + GA101 - Obinutuzumab. University of California, San Diego

infusion reaction symptoms, infusion rate escalation may resume at the increments and intervals as appropriate for the treatment dose.

6.2.7 Dosage Modification/Toxicity Management

A number of measures will be taken to ensure the safety of subjects participating in this study. These measures will be addressed through exclusion criteria (see Section 4.2) and routine monitoring as follows.

Subjects enrolled in this study will be evaluated clinically and with standard laboratory tests before and during their participation in this study. Safety evaluations will consist of medical interviews, recording of AEs, physical examinations, blood pressure, and laboratory measurements. Subjects will be evaluated for AEs (all grades), SAEs, and AEs requiring study drug interruption or discontinuation at each study visit for the duration of their participation in the study.

6.2.8 Assessment of Hematologic Toxicities

The evaluation of potential treatment-induced toxicity in subjects with advanced CLL may be quite difficult and requires careful consideration of both the manifestations of the underlying disease, as well as adverse reactions to the therapy under study. Some of the conventional criteria for toxicity are not applicable, especially under circumstances of progressive bone marrow failure from the CLL itself.

Dose modifications for hematologic toxicity in subjects with CLL must be made with consideration of the increased frequency of hematologic compromise at the initiation of therapy. Therefore, the standard criteria used for solid tumors are difficult to be applied directly; many subjects would be considered to have Grade 2-4 hematologic toxicity at presentation.

As a consequence, dose modification decisions for subjects with cytopenia (below the lower limit of the normal range) at baseline will be based on the International Workshop in CLL (IWCLL) guidelines (Hallek et al., 2008). For subjects with a normal neutrophil count, platelet count, and/or hemoglobin value at baseline, the NCI CTCAE, v4.0, will be used.

6.2.9 Administration of Granulocyte Colony-Stimulating Factor

G-CSF may be administered as primary prophylaxis in each cycle of therapy, as per the American Society of Clinical Oncology (ASCO) guidelines or each site's institutional standards.

Ibrutinib + GA101 – Obinutuzumab. University of California, San Diego

6.2.10 Hepatitis B Virus Reactivation

Active acute or chronic Hepatitis B (HBV): Subjects with acute or chronic active HBV will be defined based on CDC guidelines (Appendix 1). This will include subjects with positive serology for hepatitis B surface antigen (HBsAg) or hepatitis B core antibody (HBcAb) associated with HBV-DNA positive test by real time quantitative qPCR assessment. Subjects who are anti-HBc positive and HBV-DNA test negative, may be enrolled in the study and should undergo regular monitoring of HBV viral load using HBV-DNA qPCR. Those subjects may be referred to a hepatologist or gastroenterologist for appropriate monitoring and management.

For the subset of subjects who are Hepatitis B viral DNA negative and anti-HBc positive and have undetectable Hepatitis B viral DNA levels at screening, Hepatitis B viral DNA levels must be followed approximately every 4 weeks. Guidelines for the management of hepatitis B reactivation are outlined in Table 2.

Table 2 Management of Hepatitis B Reactivation

Hepatitis B Viral DNA Level by Real-Time PCR	Guideline
> 100 IU/mL	Hold GA101 - Obinutuzumab
	Begin anti-viral medication and treat for at least 1 year after the last dose of GA101 - Obinutuzumab.
	 Immediately refer the subject to a gastroenterologist or hepatologist for management.
	Resume GA101-Obinutuzumab once Hepatitis B viral DNA levels decrease to undetectable levels.
> 100 IU/mL while on anti-viral medication	Discontinue GA101 - Obinutuzumab.
29-100 IU/mL	Retest within 2 weeks.
	If still hepatitis B viral DNA positive:
	Hold GA101 - Obinutuzumab

Ibrutinib + GA101 – Obinutuzumab. University of California, San Diego

Begin anti-viral medication and treat for at least 1 year after the last dose of GA101 - Obinutuzumab.

 Immediately refer the subject to a gastroenterologist or hepatologist for management

 Resume GA101-Obinutuzumab once Hepatitis B viral DNA levels decrease to undetectable levels

6.2.11 Management of Infusion-Related Reactions and Anaphylaxis

Please refer to Section 6.4.4 for information relating to concomitant medications. Medications (including subcutaneous epinephrine, corticosteroids, and intravenous diphenhydramine) and resuscitation equipment should be available for immediate use.

Life-Threatening Infusion-Related Reactions and Anaphylaxis.

In the event of a life-threatening IRR (which may include pulmonary or cardiac events) or IgE-mediated anaphylactic reaction, GA101-Obinutuzumab should be discontinued and no additional GA101-Obinutuzumab should be administered (see Table 3). Subjects who experience any of these reactions should receive aggressive treatment of symptoms and will be discontinued from study treatment. Subjects will continue in follow-up until resolution of reactions or clinical stability.

Table 3 Management of Infusion-Related Symptoms

Infusion-Related Symptoms ^a	Guidance
Grades 1–2	 Interrupt or slow the rate of the infusion Give supportive treatment ^b
	Upon symptom resolution, may resume infusion rate escalation at the investigator's discretion ^c
Grade 3	Discontinue infusion until resolution of symptoms

Ibrutinib + GA101 - Obinutuzumab. University of California, San Diego

- Give supportive treatment ^b
- Upon symptom resolution, may resume infusion rate escalation, at investigator discretion ^c
- Note: If the same adverse event recurs with the same severity, treatment must be permanently discontinued.

Grade 4^d

 Discontinue infusion immediately, treat symptoms aggressively, and do not restart drug

- a Refer to National Cancer Institute Common Terminology Criteria for Adverse Events, v4.0, for the grading of symptoms http://evs.nci.nih.gov/ftp1/CTCAE/CTCAE 4.03 2010-06-14 QuickReference 8.5x11.pdf (Appendix 7)
- Subjects should be treated with acetaminophen and an antihistamine such as diphenhydramine if they have not been received these within the previous 4 hours. IV saline may be indicated. For bronchospasm, urticaria, or dyspnea, subjects may require antihistamines, oxygen, corticosteroids (e.g., 100 mg IV prednisolone or equivalent), and/or bronchodilators. For hypotension, subjects may require vasopressors.
- Upon complete resolution of symptoms, the infusion may be resumed at 50% of the rate achieved prior to interruption. In the absence of infusion related symptoms, the rate of infusion may be escalated in increments of 50 mg/hour every 30 minutes to a maximum rate of 400 mg/hr.
- d Including but not limited to anaphylaxis, acute life-threatening respiratory symptoms, or other life-threatening infusion reaction.

6.2.12 Prophylaxis Tumor Lysis Syndrome

All subjects will receive prophylaxis for tumor Lysis syndrome (TLS) in the first cycle of treatment and will return to the clinic on day 4 for laboratory assessment in order to evaluate the risk for TLS. Diagnosis of TLS and laboratory assessment will be made based on the Cairo-Bishop Laboratory definition (Coiffier B et al., 2008) (Appendix 4).

Prophylaxis for TLS includes:

Ibrutinib + GA101 – Obinutuzumab. University of California, San Diego

- Appropriate hydration consisting of a fluid intake of 2- 3 L/day starting 1 to 2 days prior to the first dose of GA101 – Obinutuzumab.
- Administration of allopurinol (300 mg/day orally) or a suitable alternative treatment starting prior to the first infusion of GA101 - Obinutuzumab (Cycle 1 Day 1).

Those subjects with laboratory evidence of TLS will be graded according to the NCI-CTCAE grading system (Version 4.0) (Appendix 4) and will return to the clinic on the day 4 of the subsequent cycles to continue follow-up of laboratory parameters.

For subjects with evidence of TLS \geq Grade 3, GA101 - Obinutuzumab and Ibrutinib should be discontinued and the subject treated as clinically indicated. A dose delay of up to 8 weeks is permitted for GA101- Obinutuzumab / Ibrutinib to allow recovery of TLS. Following the complete resolution of TLS complications, Ibrutinib and GA101 - Obinutuzumab may be re administered at the full dose during the next infusion in conjunction with prophylactic therapy. If the treatment is delayed more than 8 weeks because there is no improvement of TLS, treatment will be stopped and the subject will continue in follow-up until the beginning of new treatment or death.

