6.3.3 Ibrutinib Overdose

Any dose of study drug in excess of that specified in this protocol is considered to be an overdose. Signs and symptoms of an overdose that meet any Serious Adverse Event criterion must be reported as a Serious Adverse Event in the appropriate time frame and documented as clinical sequelae to an overdose.

There is no specific experience in the management of ibrutinib overdose in subjects. No maximum tolerated dose (MTD) was reached in the Phase 1 study in which subjects received up to 12.5 mg/kg/day (1400 mg/day). Healthy subjects were exposed to up to single dose of 1,680 mg. One healthy subject experienced reversible Grade 4 hepatic enzyme increases (AST and ALT) after a dose of 1,680 mg. Subjects who ingested more than the recommended dosage should be closely monitored and given appropriate supportive treatment. Refer to Section 11.4.3.8 for further information regarding special reporting situations as a result of overdose

Ibrutinib + GA101 - Obinutuzumab. University of California, San Diego

Dose Modifications and delays for GA101 – Obinutuzumab

Splitting the first dose of GA101 – Obinutuzumab in Cycle 1 is mandatory. The first dose (1,000 mg) must be administered over Days 1 and 2 (100 mg on Day 1 and 900 mg on Day 2). Infusions should be interrupted or slowed if subjects experience infusion reactions (see Section 6.2.11). If a planned dose of GA101 - Obinutuzumab is missed, it should be administered as soon as possible and the next cycle should begin 28 days later. Do not wait until the next planned dose.

No reduction in the dose of GA101 - Obinutuzumab is allowed. A dose delay of up to 8 weeks is permitted for GA101 - Obinutuzumab to allow recovery of hematologic toxicities to \leq Grade 2 or non-hematologic toxicities to Grade 1 or baseline level. If the treatment is delayed for more than 8 weeks because there is no improvement of cytopenia to \leq Grade 2, treatment under this protocol will be discontinued and the subject will continue in follow-up until the beginning of new treatment or death.

If a subject experiences grade 3 or 4 cytopenia, the guidelines for GA101 – Obinutuzumab and Ibrutinib dose-delay are outlined in Table 7:

Table 7 Dose Modification for Cytopenias

Grade	GA101 - Obinutuzumab	Ibrutinib

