7. CRITERIA FOR SUBJECT DISCONTINUATION

Subjects will remain on study for three years after completion of the last cycle of treatment or until they have progressive disease requiring further treatment or death.

Subjects who meet the following criteria should be discontinued from the study:

Ibrutinib + GA101 – Obinutuzumab. University of California, San Diego

- HBV Reactivation that is not responding to appropriate management and antiviral therapy as described in section 6.2.10, or subjects with evidence of HBV associated hepatitis with LFT abnormalities. Subjects who are carriers of hepatitis B at the time of discontinuation from study treatment will continue to be followed for clinical and laboratory signs of active HBV infection and for signs of hepatitis.
- Severe or life-threatening anaphylaxis or hypersensitivity reaction
- Progressive Disease: Subjects with PD will discontinue the study treatment but will continue in follow-up until the beginning of new treatment or death.
- Severe life threatening reactions to GA101 Obinutuzumab or Ibrutinib administration.
- Medical Prudence/Non-Compliance: The Principal Investigator may remove a subject from study any time deemed medically prudent to do so to assure the subject's health and welfare. A subject will also be removed from study to preserve the integrity of the investigation. The latter includes incidents in which the subject frequently misses study appointments needed to accurately assess response/adverse reactions, or is non-compliant with study directions provided by the investigator or study personnel. "Inevaluable" subjects will be replaced to meet target accrual.

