Based on this, we will use a Simon's two-stage optimal design in this study (Simon, 1989). The null hypothesis that the true overall response rate is 78% will be tested against a one-sided alternative. In the first stage, 10 subjects will be accrued. If there are 8 or fewer responses in these 10 subjects, the study will be stopped. Otherwise, 22 additional subjects will be accrued for a total of 32. The null hypothesis will be rejected if 29 or more responses are observed in 32 subjects. This design yields a type I error rate of 5% and power of 80% when the true response rate is 94%.

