10.6 PLANNED EFFICACY EVALUATIONS

- Phase IB: We will evaluate AE and determine DLTs as described in Section 10.2.
- Phase II: All treated subjects will undergo evaluation for response to treatment 2 months after completion of study treatment. Evaluation tests will include CT / MRI of the chest, abdomen and pelvis, CMP, CBC, LDH, bone marrow biopsy including immunohistochemistry for pathology analysis, FISH and chromosome analysis as well as multiparameter (4 colors) flow cytometry for MRD analysis.

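### Follow-up after a stop for a life-threatening infusion reaction, hypersensitivity, another life-threatening drug reaction or unresponsive HBV reactivation is contradictory, and one reading loses response and survival data

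*Combined protocol and SAP*

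**What the plan says.** **Stops with short or unstated follow-up.** Section 6.2.11 takes a subject with a life-threatening infusion-related reaction (IRR) or anaphylaxis off study treatment and adds: "Subjects will continue in follow-up until resolution of reactions or clinical stability". Section 7 opens its list with "Subjects who meet the following criteria should be discontinued from the study". The list includes severe or life-threatening anaphylaxis or hypersensitivity, severe life-threatening reactions to either drug, and hepatitis B reactivation that does not respond to management. The two reaction bullets have no follow-up clause. The hepatitis B bullet keeps monitoring for hepatitis B only.

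**Stops with full follow-up.** For unresolved TLS, Section 6.2.12 says "treatment will be stopped and the subject will continue in follow-up until the beginning of new treatment or death". For unresolved cytopenia, the obinutuzumab dose-delay text after Section 6.3.3 says "treatment under this protocol will be discontinued and the subject will continue in follow-up until the beginning of new treatment or death". The ibrutinib column of Table 7 also mentions assessment of TFS and OS. The progression bullet in Section 7 stops treatment but continues follow-up to new treatment or death.

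**General rules.** Section 10.6 says "All treated subjects will undergo evaluation for response to treatment 2 months after completion of study treatment". Section 3.1.1 determines response in all subjects who received treatment. Section 9.5 follows subjects to new treatment, withdrawal of consent or death. Section 9.6 defines end of study as new CLL treatment or withdrawal of consent.

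**Analysis rules.** The Efficacy Population (10.3.2) requires at least one post-baseline efficacy assessment. Section 10.4 does not replace phase II subjects who withdraw for toxicity.

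**The concern.** How long a subject is followed appears to depend on which toxicity ended treatment, and the plan gives no reason for the difference. An infusion reaction can end treatment at the first infusion. If the site then releases the subject once the reaction settles, there is no CT or marrow response assessment and no record of progression, next treatment or survival, although consent was never withdrawn.

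Such a loss would be informative, because the reason for it is intolerance of the regimen. The subject may have no post-baseline efficacy assessment, would then fall outside the Efficacy Population, and is not replaced. The ORR and the Kaplan-Meier curves would then lean towards subjects who tolerated treatment. Data not collected cannot be recovered at analysis.

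The protocol's background shows the pattern. In Study BO21003 (Section 1.3.2.1), one of five CLL subjects withdrew at Cycle 1 Day 1 with a Grade 4 IRR, and efficacy assessments were available only for the other four.

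**Working it through.** **1. Passages side by side**

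| Reason for stopping | Specific rule | Follow-up stated there |
|---|---|---|
| Life-threatening IRR, anaphylaxis | 6.2.11; Section 7 | Resolution or clinical stability; listed as off study |
| Other life-threatening drug reaction | Section 7 | None; listed as off study |
| Unresponsive HBV reactivation | Section 7 | HBV monitoring only; listed as off study |
| TLS | 6.2.12 | New treatment or death |
| Cytopenia | Dose-delay text, Table 7 | New treatment or death |
| Progression | Section 7 | New treatment or death |
| Any treated subject | 3.1.1, 9.5, 9.6, 10.6 | Response assessment; then new treatment, consent withdrawal or death |

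The first three rows conflict with the last. Recurrent Grade 3 IRR, for which Table 3 ends treatment permanently, has no specific follow-up rule.

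**2. Reproducing the design**

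Inputs from Section 10.3.4: "The null hypothesis that the true overall response rate is 78% will be tested against a one-sided alternative"; "If there are 8 or fewer responses in these 10 subjects, the study will be stopped"; "The null hypothesis will be rejected if 29 or more responses are observed in 32 subjects". The target ORR is 94%.

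The trial continues with 9 or 10 responses in 10, and then needs 20 or 19 of the next 22:

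P(reject) = P(X1=9)·P(X2≥20) + P(X1=10)·P(X2≥19), with X1 ~ Bin(10, p) and X2 ~ Bin(22, p).

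- p = 0.94: 0.3438 × 0.8576 + 0.5386 × 0.9602 = 0.812.
- p = 0.78: 0.2351 × 0.1081 + 0.0834 × 0.2542 = 0.0466.

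Both agree with the stated 80% power and 5% type I error. The slack is 32 − 29 = 3 non-responders overall, and 10 − 9 = 1 in stage 1.

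**3. Illustration of the loss**

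The documents give no rate for these stops, so q is assumed. If stopped subjects are unassessed and count as non-responders while all others respond at 94%, the effective rate is p = 0.94(1 − q). If they are assessed and half respond (also an assumption), p = 0.94(1 − q) + 0.5q.

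| q | Expected stops in 32 | p, unassessed | Power, unassessed | p, half respond | Power, half respond |
|---|---|---|---|---|---|
| 1% | 0.32 | 0.9306 | 0.750 | 0.9356 | 0.784 |
| 2% | 0.64 | 0.9212 | 0.683 | 0.9312 | 0.754 |
| 3% | 0.96 | 0.9118 | 0.615 | 0.9268 | 0.723 |
| 5% | 1.60 | 0.8930 | 0.480 | 0.9180 | 0.660 |

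Only the gap between the two power columns could be recovered by assessment under that assumption. The full gap to 0.812 is the upper bound, reached if stopped subjects would respond as often as the rest.

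**4. Single losses**

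- One unassessed subject in stage 1: all nine others must respond, 0.94^9 = 0.573, against 0.882 (0.3438 + 0.5386) with ten assessed.
- One unassessed subject in stage 2, threshold kept at 29: 31 remain and power is 0.689.

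**The case against.** The strongest reply is that nothing is lost. Section 6.2.11 speaks of leaving study treatment, not the study, and does not say that follow-up is limited to the reaction. Its sentence sits in a reaction-management section and resembles the SAE rule in Section 11.3.4, which follows an event until it resolves or stabilizes. It can therefore be read as a minimum for safety follow-up. The Section 7 lead-in also covers progression, where follow-up expressly continues, and its hepatitis B bullet speaks of discontinuation from study treatment. The Synopsis moves subjects from treatment to follow-up on drug discontinuation and lists no toxicity among the reasons follow-up ends.

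This stands to the extent that data loss is one reading, not a certainty. It does not remove the contradiction. The progression bullet states that follow-up continues and the reaction bullets do not, so a site can fairly read the latter as full exit.

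A reader might infer two stronger conclusions:

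- **That toxicity stops in general lose response, PFS and OS data.** The documents do not support this: TLS and cytopenia stops are toxicity stops and are followed.
- **That power falls to 31% or 19%, by applying the background rates 3/38 or 4/38.** The arithmetic is right (0.309 and 0.193), but the rates do not measure these events. The 3/38 are IRR withdrawals with no grade given, and the 4/38 are withdrawals for any adverse event. The 4/51 in the previously untreated monotherapy study includes one neutropenia and one thrombocytopenia stop, leaving at most two infusion-type stops. The untreated combination study (41 subjects) lists no IRR among nine discontinuations, and the CLL11 run-in had no severe IRR in six. Pooling gives at most (3 + 2 + 0 + 0)/(38 + 51 + 41 + 6) = 5/136 = 3.7%, any grade, or about 1.2 of 32 subjects.

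**Conclusion.** The concern holds as a contradiction to reconcile, confined to stops for life-threatening infusion reactions, anaphylaxis or hypersensitivity, other life-threatening drug reactions and unresponsive hepatitis B reactivation. Read literally, 6.2.11 and Section 7 end efficacy and survival follow-up for these subjects. The general sections keep it.

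Only a few subjects are likely to be affected, but the decision rule has little slack. The fall in power from 81% to between 75% and 48% for assumed stop rates of 1% to 5% is an illustration. It rests on three assumptions that the protocol does not state: the stop rate, counting unassessed subjects as non-responders (10.3.2 might instead exclude them), and a 94% response rate in everyone else. It overstates what assessment could recover if stopped subjects respond less often, or if the 94% target already allows for such stops. The bias in PFS, TFS and OS cannot be sized from the documents, which also state no censoring rule for these subjects.

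**What to change.** Reconcile 6.2.11 and Section 7 with 9.5, 9.6 and 10.6:

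- State once that stopping study treatment for toxicity is not leaving the study, and word the relevant Section 7 bullets as discontinuation from study treatment.
- State that any treated subject who stops for toxicity and has not withdrawn consent has the planned response assessment, then the same efficacy and survival follow-up as the TLS and cytopenia stops. Say how that assessment is timed after an early stop, since 10.6 counts from completion of treatment.
- State that follow-up to resolution or clinical stability governs adverse-event follow-up only.
- In 10.3.2 and 10.3.3, say how a treated subject with no response assessment counts in the ORR and is censored for PFS, TFS and OS.

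The cost is protocol wording plus already-planned assessments for a few subjects, with some visit burden for people off treatment. No rule on stopping treatment or managing reactions changes.
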